### **2.3.2 Randomization and allocation methods**

The randomization service contract organization should prepare randomization key code tables in accordance with predefined procedures for creation and storage of randomization key code tables. Subjects who are judged to be eligible for transition to the treatment period will be assigned to treatment groups based on the randomization key code table in the Web registration system, and the assignment number should be notified on the Web registration system. Details of the randomization shall be specified in the enrollment center subject allocation specifications. Subjects should be randomly assigned in a 1:1 ratio to MT-6548 and darbepoetin groups.

## Evaluation time point

Item	Visit	Informed consent	Screening period [a]		Treatment period [b]												Final day of the follow-up observation [c]				
			Treatment period Phase 1		Treatment period Phase 2						Treatment period Phase 2										
			First day	Visit 2	First day	W2	W4	W6	W8	W10	W12	W16	W20	W24	W28	W32	W36	W40	W44	W48	W52
Visit number	IC	SV1	SV2	TV1	TV2	TV3	TV4	TV5	TV6	TV7	TV8	TV9	TV10	TV11	TV12	TV13	TV14	TV15	TV16	TV17	TV18
Permitted range (days)	-	-	-	-	-	-	-	-	-	-	-	-	-	-	-	-	-	-	-	-	-
Procedure/evaluation																				-7 or +14 [d]	-7
Informed consent		X																			
Inclusion/exclusion criteria		X	X	X																	
Allocation																					
Patient background and history		X																			
Height			X																		
Dry weight, body weight [e]			X																		
Folic acid and vitamin D; [f]		X																			
Pregnancy test [g]		X	X [g]	X																	
Hematology test [g], [h], [i]		X		X																	
Blood Biochemistry test [f], [h], [k]		X		X																	
C-reactive protein [f], [k]		X		X																	
Iron-related measures [f], [k]		X		X																	
Haptocidin [k]			X	X	X																
EPO [g]			X	X	X																
VEGF [k]			X																		
DHEA-S [k]			X																		
Vital signs [g], [k], [l]		X	X	X	X																
Rating standard 12-lead ECG [h], [m]			X																		
Endoscopy [d]			X																		
Chest X-ray [d]			X																		
Duration of hemodialysis				X																	
QOL measures (EQ-5D-5L, KIDQOL)				X																	
AE investigations [g]				X	X	X	X	X	X	X	X	X	X	X	X	X	X	X	X	X	
Blood sampling for PK testing					X																
Blood sampling for genetic analysis [o]						X															
Blood sampling for plasma's protein binding test [p]						X															
Product evaluation/procedure							X	X	X	X	X	X	X	X	X	X	X	X	X	X	
Investigation of concomitant medications/therapies								X	X	X	X	X	X	X	X	X	X	X	X	X	
AT-6548 tablets [q], [r], [s]									X	X	X	X	X	X	X	X	X	X	X	X	
Darbepoetin alfa injection [r], [t]										X	X	X	X	X	X	X	X	X	X	X	
Iron supplements											X										

Blood sampling for genetic analysis performed once as early as possible after Week 7 of treatment period

Administered according to the dosage adjustment guidelines

Administered according to the dosage adjustment guidelines

Iron supplements administered to maintain a serum ferritin level of 2100 ng/ml or a T-SAT of ≥20%

- [a] The screening period can be up to 6 weeks. Test results should be reviewed prior to transition from the first day of the screening period to screening period Visit 2 and from screening period Visit 2 to the first day of the treatment period. Re-testing can be performed as necessary.
- [b] The scheduled study visit during the treatment period shall be the dialysis day 2 days after the previous dialysis, and if it is difficult, the dialysis day 1 day after the previous dialysis.
- [c] Should not be performed if discontinued before the treatment period.
- [d] Fundoscopy and chest X-ray should be performed once during the screening period. Fundoscopy and chest X-ray should be performed once during Weeks 20–24 of the treatment period, and once during Weeks 48–52 of the treatment period. Should be performed within 14 days after discontinuation whenever possible if discontinued during the treatment period.
- [e] Body weight should be measured before and after dialysis.
- [f] Measurements on the day of dialysis should be performed before dialysis during the screening period.
- [g] Tests during the treatment period should be performed before dialysis on the day of dialysis.
- [h] To be performed only in female subjects of childbearing potential.
- [i] Hb values should be measured in blood collected in the supine position.
- [j] Only Hb values should be measured.
- [k] Only urea nitrogen values will be measured before and after dialysis on the first day, Week 24, and Week 52 of the treatment period and on the day of treatment discontinuation.
- [l] Measurements should be made before blood sampling as much as possible. Measurements should be made in the sitting position after 5 minutes of rest.
- [m] Measurements should be made before blood sampling as much as possible. Measurements should be made in the supine position after 5 minutes of rest.
- [n] AE investigation should begin after study drug administration.
- [o] Blood should be collected once as early as possible after Week 2 of the treatment period for subjects who have given consent to the genetic analysis tests.
- [p] For subjects giving consent to the plasma protein binding rate study, blood should be collected once before study drug administration. Blood collection should be performed before dialysis on the day of dialysis.
- [q] MT-6548 tablets should be prescribed to subjects depending on the number of their unused tablets. Subjects should be instructed to use up one bottle before opening the next.

- [r] In principle, dosage adjustments should be performed at scheduled study visits or on the day of darbepoetin alfa injection; however, an additional visit may be provided for dosage adjustment, if considered necessary, in cases where excessive increases or decreases in Hb values are of concern based on the Hb time course.
- [s] The first dose should be administered after completion of the scheduled tests on the first day of the treatment period.
- [t] The first dose should be administered after completion of the scheduled tests on the first day of the treatment period. However, the tests scheduled after dialysis should be performed before the first dose whenever possible.

## 2.4 Rationale for sample size

A total of 300 subjects (150 each for the MT-6548 and darbepoetin groups) should be enrolled in the treatment period.

### [Rationale]

For the primary efficacy endpoint of mean Hb values at treatment period Weeks 20 and 24, the mean Hb value in the darbepoetin group is assumed to be 11.0 g/dL, the difference between the MT-6548 and darbepoetin groups is assumed to be 0 g/dL, and the standard deviation for both is assumed to be 1.73 g/dL. The non-inferiority margin is set at -0.75 g/dL. Calculation of statistical power from these assumptions shows that a sample size of 150 subjects in each group would ensure greater than 95% probability that the mean of mean Hb values in the MT-6548 group and their 95% CI would fall within the target Hb range (10.0–12.0 g/dL) and non-inferiority could be established.

The assumed standard deviation was set at 1.73 g/dL based on the upper limit of the two-sided 95% confidence interval of the standard deviation in the MT-6548 300 mg group at Week 6 in study CI-0022.

## 3. Endpoints

### 3.1 Efficacy endpoints

#### 3.1.1 Primary endpoint

Mean Hb values at Weeks 20 and 24 of the treatment period

#### 3.1.2 Secondary endpoints

- (1) Hb values at each evaluation time point in the treatment period

- (2) Proportion of subjects with mean Hb values within the target range (10.0 to <12.0 g/dL), <10.0 g/dL, and  $\geq 12.0$  g/dL at each evaluation time point in the treatment period

### 3.1.3 Other endpoints

- (1) Number of days to maintain the target Hb values
- (2) Proportion of subjects receiving rescue therapy with ESA formulations, red blood cell transfusion, or phlebotomy
- (3) Study drug dosage
- (4) MT-6548 group only: total number of MT-6548 tablet dosage adjustments
- (5) Iron supplement dosage
- (6) Proportion of subjects receiving oral, intravenous, or (any route) administration of iron supplements
- (7) Proportion of subjects with serum ferritin  $\geq 100$  ng/mL or TSAT  $\geq 20\%$ .
- (8) Changes and rate of changes in iron-related indices (serum iron, TIBC, TSAT, and serum ferritin levels) and hepcidin from the first day of the treatment period
- (9) Changes in hematocrit, red blood cell count, reticulocytes (count and rate), mean corpuscular volume, mean corpuscular hemoglobin, and erythropoietin from the first day of the treatment period
- (10) Changes and rate of changes in systolic blood pressure, diastolic blood pressure, lipids (total cholesterol, LDL-C, HDL-C, LDL-C/HDL-C ratio, triglycerides), and blood glucose from the first day of the treatment period
- (11) QOL indices (EQ-5D-5L, KDQOL)

## 3.2 Safety endpoints

- (1) Adverse events and adverse drug reactions

- (2) Laboratory test values

- 1) Hematology tests:

Mean corpuscular volume, mean corpuscular hemoglobin, mean cell hemoglobin concentration, RBC distribution width, WBC count, WBC fractions (neutrophils, eosinophils, monocytes, lymphocytes, basophils), platelet count

- 2) Blood biochemistry tests:

Total protein, albumin, blood glucose, urea nitrogen, creatinine, uric acid, CPK, total bilirubin, AST, ALT, ALP, LDH,  $\gamma$ -GTP, Na, K, Cl, Ca, P, Mg, bicarbonate, total cholesterol, LDL-C, HDL-C, triglycerides

- 3) C-reactive protein
- 4) Folic acid and vitamin B12
- 5) Vascular endothelial growth factor (hereinafter, VEGF)
- 6) Dehydroepiandrosterone sulfate (hereinafter, DHEA-S)

(3) Resting standard 12-lead ECG

(4) Dry weight

(5) Body weight

(6) Vital signs

(7) Fundoscopy

(8) Chest X-ray

(9) Proportion of subjects with documented Hb values of  $\geq 12.0$  g/dL or  $\geq 13.0$  g/dL

(10) Proportion of subjects with documented Hb values of  $< 9.0$  g/dL or  $< 8.0$  g/dL.

(11) Proportion of subjects with a documented Hb increase rate of  $> 0.5$  g/dL/week

(12) Hb value after dose reduction or interruption of the study drug

(13) Kt/V

### 3.3 Pharmacokinetic endpoints

Plasma concentrations of unchanged MT-6548

## 4. Definition of Derived Variables

### 4.1 Age at consent acquisition

Age (year) = Date of consent acquisition (year) – Date of birth (year)

However, when (Date of consent acquisition [month] < Date of birth [month]) or (Date of consent acquisition [month] = Date of birth [month] and Date of consent acquisition [days] < Date of birth [days]), 1 is subtracted from the traditional Japanese age system calculated above.

## 4.2 Duration of disease

The duration of disease (year) should be the period from the onset of renal anemia to the consent month and shall be the integer part + 1 digit (rounded). Duration of disease is calculated as follows:

Duration of disease (year) = (Date of consent acquisition [year] – Time of onset [year]) + (Date of consent acquisition [month] – Time of onset [month])/12

If the month of onset is unknown, the month is calculated as 1.

## 4.3 Period from the first day of hemodialysis

The period from the start of hemodialysis (year) should be the period from the start of hemodialysis (time of first hemodialysis or hemodiasfiltration) to the month of consent acquisition and should be the integer part + 1 digit (rounded). The period from the start of hemodialysis should be calculated as follows:

Period from the start of hemodialysis (year) = (Date of consent acquisition [year] – Start of hemodialysis [year]) + (Date of consent acquisition [month] – Start of hemodialysis [month])/12

If the month of the start of hemodialysis is unknown, the month should be calculated as 1.

## 4.4 BMI

BMI (kg/m^2) = Dry weight (kg)/(Height [m])

Should be rounded and displayed to one decimal place.

## 4.5 LDL-C/HDL-C ratio

LDL-C/HDL-C ratio = LDL-C (mg/dL)/HDL-C (mg/dL)

Should be rounded and displayed to two decimal places.

## 4.6 Number of days of drug interruptions

The number of days of drug interruptions does not include subject's forgetting to take the drug and is defined by the following formula.

Number of days of drug interruptions (days) = Day of resumption of study drug administration – First day of study drug interruption

If there are multiple interruptions, the sum of them should be used.

Resumption date of study drug administration: After the entry of "Daily Dose" = 0 mg or 0 µg in the CRF, the first dose should be taken when a value of >0 mg is entered for the first time or should be administered when a value of >0 µg is entered for the first time. If the drug interruption continues until

Week 24 of the treatment period, days should be calculated based on the visit date after Week 24 of the treatment period as the resumption date. Specifically, if the treatment is completed or discontinued while the drug is interrupted, the day before the day of blood sampling at Week 24 for hematology tests or the day before the day of treatment discontinuation should be used.

First day of study drug interruption: The day of administration when "Daily Dose" = 0 mg or 0 µg is first entered in the CRF.

#### **4.7 Study drug administration/treatment duration**

For subjects who completed treatment period phase I:

Study drug administration/treatment duration (days) = Day of blood sampling for hematology tests at Week 24 – First day of the treatment period

For subjects who discontinued:

Study drug administration/treatment duration (days) = Day of discontinuation – First day of the treatment period

#### **4.8 Study drug administration/number of administration days**

The number of days that the study drug is taken (administered) is defined by the following formula.

Number of MT-6548 administration days (days) = Period of study drug administration – Number of days of no study drug administration other than drug interruptions – Number of days of drug interruptions

Number of darbepoetin alfa administration days (days) = Number of doses of darbepoetin alfa once every week × 7 days + Number of doses of darbepoetin alfa once every 2 weeks × 14 days + Number of doses of darbepoetin alfa once every 4 weeks × 28 days

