#### **4.9 Study drug administration/compliance rate**

Drug administration/compliance rate (%) = Number of days of study drug use (administration)/(Period of study drug use [administration] – Number of days of drug interruptions) × 100

However, if the compliance rate exceeds 100%, it should be 100%.

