#### (2) PPS

PPS is defined as the analysis set consisting of subjects from the FAS excluding the following subjects:

- ✓ Subjects who deviated from inclusion criteria
- ✓ Subjects who met any of the exclusion criteria

- ✓ Subjects who violated rules concerning prohibited concomitant drugs or therapies
- ✓ Subjects with a <80% compliance rate for either MT-6548 150 mg tablets or darbepoetin alfa injection

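### Darbepoetin compliance credits injection days that lie outside its own denominator, so some under-dosed darbepoetin subjects can stay in the per-protocol set (minor)

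*SAP*

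**What the plan says.** The SAP file holds a plan for the Phase 1 data and a plan for the final data. Both define darbepoetin compliance in the same way.

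- **Numerator (4.8).** It begins "Number of darbepoetin alfa administration days (days) = Number of doses of darbepoetin alfa once every week" times 7 days and adds 14 days per two-weekly dose and "Number of doses of darbepoetin alfa once every 4 weeks × 28 days". No rule shortens an injection's credit.
- **Rate (4.9).** "Number of days of study drug use (administration)/(Period of study drug use [administration] – Number of days of drug interruptions) × 100". It is then capped: "However, if the compliance rate exceeds 100%, it should be 100" percent.
- **Period (4.7).** For discontinued subjects: "Study drug administration/treatment duration (days) = Day of discontinuation – First day of the treatment period". For Phase 1 completers: "Day of blood sampling for hematology tests at Week 24 – First day of the treatment period". The final SAP uses Week 52 sampling.
- **Interruptions (4.6).** "Number of days of drug interruptions (days) = Day of resumption of study drug administration – First day of study drug interruption". For darbepoetin these days leave the denominator only.
- **MT-6548 (4.8).** Administration days are the period minus untaken days minus interruption days.
- **Uses.** The Phase 1 PPS (5.1) drops subjects with a below-80% "compliance rate for either MT-6548 150 mg tablets or darbepoetin alfa injection". Section 8.4 of both SAPs tabulates compliance by arm, split at 80%. Phase 1 section 8.5.1 repeats the primary analysis in the PPS to examine robustness.
- **Truncation elsewhere.** For mean weekly dose, note *5 to section 4.10 ends the last injection's period by the day before discontinuation.

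**The concern.** A compliance rate should count covered days only inside the window used as its denominator. Here the darbepoetin numerator can extend past that window, by up to one dose interval minus a day (6, 13 or 27 days) at each discontinuation or mid-interval interruption. A late final visit has a similar effect. Those surplus days can stand in for a missed injection.

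The MT-6548 rate is (period − interruptions − untaken days)/(period − interruptions), which cannot exceed 100% and has no such surplus. The two arms are therefore measured by rules that are not equivalent, and the error runs towards overstating darbepoetin compliance. At stake are the like-for-like reading of the by-arm compliance table and, in Phase 1, whether the 80% rule removes the subjects it is meant to remove from the robustness analysis.

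**Working it through.** The documents give no compliance result to reproduce, so the check applies the formulas to dosing histories.

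**Conventions and assumptions.** The first injection is on Day 0, as in protocol Table 9.1-1. Injections are due every 7, 14 or 28 days before the end day. The period in 4.9 is taken to be the duration in 4.7. Three rates are compared:

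- SAP rate = injections given × interval / (period − interruption days).
- Days covered = the same, with credit stopped at the end of the period and at the start of an interruption.
- Injections given / injections due.

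**Baseline.** For a 168-day completer with full adherence, 24 × 7 = 12 × 14 = 6 × 28 = 168, so the SAP rate is 100%. With one missed injection it is 95.8%, 91.7% or 83.3% (weekly, two-weekly, four-weekly), and days covered gives the same values. The formula is right in this case.

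**Case A: discontinuation.** Every 4 weeks, dosed Days 0, 28 and 84 (Day 56 missed), discontinued Day 90.
- SAP: 3 × 28 / 90 = 93.3%
- Days covered: (28 + 28 + 6) / 90 = 62/90 = 68.9%
- Given/due: 3/4 = 75%

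**Case B: late Week 24 visit.** Every 4 weeks, sampled on Day 175 (the permitted window is Days 161–175). Seven injections are due, two between the first and last are missed, and Day 168 is given.
- SAP: 5 × 28 / 175 = 80.0%, which stays in the PPS because only rates below 80% are excluded
- Days covered: (4 × 28 + 7) / 175 = 119/175 = 68.0%
- Given/due: 5/7 = 71%

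**Case C: mid-interval interruption.** Every 4 weeks, interrupted Days 42–70, completed Day 168, so the denominator is 168 − 28 = 140. Injections are due on Days 0, 28, 70, 98, 126 and 154.
- None missed: 6 × 28 / 140 = 120%, capped to 100%; days covered 100%
- Day 98 missed: 5 × 28 / 140 = 100%; days covered 112/140 = 80%
- Days 98 and 126 missed: 4 × 28 / 140 = 80.0%; days covered 84/140 = 60%; given/due 4/6 = 67%

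Part of the surplus in Case C comes from the Day 154 injection running past Day 168. If the zero dose is instead entered on a due day (interruption Days 56–84, Day 112 missed), the SAP rate and days covered are both 112/140 = 80.0%.

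**How wide the gap is.** Take a four-weekly subject with one missed injection, the first and last given, who discontinues on Day D before Day 168. Days covered is (D − 28)/D, below 80% for every D under 140. The SAP rate is at least 80% on Days 57–70 (56/D), 85–105 (84/D) and 113–139 (112/D). That is 14 + 21 + 27 = 62 of 111 possible days. In the third range given/due is 4/5 = 80%, so both measures fail on 14 + 21 = 35 of 111. On days covered alone, the two-weekly count is 30 of 139 and the weekly count 14 of 153. These are counts of calendar days, not of subjects.

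**The case against.** The strongest reply is that multiplying doses by interval is a convention, not a miscalculated figure, and that the SAP never defines compliance as truncated days covered. Some apparent misclassifications do depend on the measure. A two-weekly subject with one of five injections missed who discontinues on Day 58 has SAP 56/58 = 96.6% and days covered 44/58 = 75.9%, but given/due 4/5 = 80.0%, which properly stays in the PPS. If the missed injection is the last one, on Day 56, days covered equals the SAP rate. This stands, and it is why the point rests on histories that fail both measures.

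The interruption route also needs a zero dose entered between injections. Section 4.6 can be read as starting the interruption on a due injection day, and then there is no overlap. That limits the route but does not close it, because protocol section 8.3.3 allows adjustments at scheduled visits.

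A reader might infer that the 100% cap generally hides missed injections. It does not. It plays no part in Cases A and B, and at a fixed interval discontinuation alone never brings a subject with a miss to 100%. It can conceal a miss only when credit runs into an interruption or the interval is shortened.

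A reader might also infer that the non-inferiority result is undermined. The documents do not support that. The primary analysis uses the FAS. A subject who stops on Day 90 has no Week 20 or 24 Hb and, with no imputation in the MMRM, informs the PPS contrast only through earlier visits. Injections are given intravenously on dialysis days, so a missed one that is not an interruption is plausibly uncommon. The final SAP has no PPS, so there only the descriptive table is affected.

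**Conclusion.** The formula is wrong as written, but the error is minor. Followed literally, it overstates darbepoetin compliance when a subject discontinues, has the final visit after the nominal day, or is interrupted mid-interval. Cases A and B fail the 80% cut on both days covered and injections given/due, yet the Phase 1 SAP retains them at 93.3% and 80.0%.

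The consequence is confined to Phase 1 PPS membership and the section 8.4 compliance tables in both SAPs. The number of subjects cannot be derived from the documents. It is likely to be small, because a missed injection has to coincide with one of these events. The conclusion assumes that sections 4.6 to 4.9 are programmed as printed, with no unwritten truncation.

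**What to change.** In section 4.8 of both SAPs, end each injection's credited days at the earliest of its dose interval, the end of the treatment period (discontinuation or final sampling day) and the start of any interruption. This matches the principle already in note *5 to section 4.10.

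Do not also cut credit at the next injection. A weekly subject who alternates 5- and 9-day gaps and misses nothing would then score (5 + 7)/14 = 86%. Keep the 100% cap for early injections and shortened intervals. A small surplus remains there. For example, a change from four-weekly to two-weekly dosing on Day 14 credits 28 + 11 × 14 = 182 days against 168, so one later miss still gives 168/168 = 100%.

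The cost is a short formula change. Injection dates and dose intervals are already recorded in the CRF (protocol 9.2.2.2). If data are already fixed, rerun the compliance tables and Phase 1 PPS membership under the amended rule and report any change. The only downside is that a few darbepoetin subjects may leave the PPS.
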